4.2.3 Secondary Objective – LV Lead Related Complication Rates

Complication rates for complications related to the LV lead

[figure not shown]
The objective is to characterize the complication rate of the QuickFlex®µ 1258T lead, and to perform a trend analysis of all complications. All complications will be evaluated for their relationship to the LV lead, reported and summarized for all patients and will also be broken out by gender. In addition, separate summaries will be presented for rollover patients and newly enrolled patients. The following complications will be reported as related to the LV lead:

- Cardiac perforation
- Lead dislodgement that occurred greater than 30 days after implant
- Lead insulation damage
- Lead fracture
- Diaphragmatic/Phrenic nerve stimulation
- Abnormal LV lead performance (abnormal lead pacing impedance, elevated pacing thresholds, and loss of capture)
- Other unexpected complications that are considered related to the LV lead

Table 2: Summary of LV Lead Related Complications

Description of Complication	Number of Patients with Comp (No. of pts = X)	% of Patients with Comp	Number of Comps	# Comps/pt-years (Total pt-years = X)
Cardiac perforation	X	X%	X	X
Lead dislodgement that occurred greater than 30 days after implant	X	X%	X	X
Lead insulation damage	X	X%	X	X
Lead fracture	X	X%	X	X
Abnormal LV lead performance	X	X%	X	X
Diaphragmatic/Phrenic nerve stimulation	X	X%	X	X
Other unexpected complications that are considered related to the LV lead	X	X%	X	X
Total	X	X%	X	X

Sample Size

[REDACTED]

[REDACTED]

[REDACTED]

Sample size accounting for patient attrition

[REDACTED]

Patient Group

[figure not shown]
All patients who are implanted or attempted to be implanted with the QuickFlex®µ 1258T LV Lead will be included in this analysis.

Analysis and reporting

Interim Reports and Trend Analysis

[REDACTED]

⁴ Hahn, G.J. and Meeker, W.Q. Statistical Intervals: A Guide for Practitioners. Wiley Series in Probability and Mathematical Statistics. 1991.

[REDACTED]

[figure not shown]
[REDACTED]

Final Report

The number and proportion of patients who experience each type of complication in Table 2 at 5 years will be presented, along with the 95% confidence intervals for the proportion based on the Clopper-Pearson exact Binomial method.

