4.0 Clinical Protocol

4.1 Study Design and Scope

The QuickFlex®µ 1258T LV Lead study is a multi-center post-approval study that will be performed in compliance with the Conditions for Approval as agreed upon with the FDA. Patients may be enrolled in the study in one of two ways. Patients who previously participated in the QuickFlex®µ 1258T LV Lead IDE study and are at a center that is participating in the post approval study may be approached for enrollment into the post approval study. In addition, newly implanted patients will be approached at participating centers for participation in the study until the enrollment criteria is met. New patients who meet inclusion/exclusion criteria will have an attempted implant of the QuickFlex®µ 1258T lead. Patients who have an unsuccessful implant will be followed for 30 days for any adverse events and then withdrawn from the study, or may have an implant reattempted if the physician chooses to do so. Patients who have a successful implant of the LV lead will be considered to have received a successful CRT-D system. Following enrollment, patients will be followed at 6 months, and every 6 months thereafter, for 60 months of follow up (5 years). After patients complete 60 months of follow-up, their participation in the study will be terminated. There will be 1,884 new patients enrolled in the study to achieve an evaluable sample size of 1036 patients. In addition, every effort will be made to enroll existing IDE patients from sites participating in the Post Approval study. [REDACTED]

[REDACTED] for a total sample size of 1,955 to 1,991 patients. [REDACTED]

[REDACTED] If implantation rate at a study site is higher than the projected estimates, then the study enrollment period will be decreased proportionately. Reporting will occur per section 4.2.3 of the protocol. In order to accomplish this, the study will be conducted at a maximum of 80 study centers.

Definitions: The following definitions will be used in the QuickFlex®µ 1258T post approval study.

Abnormal Lead Pacing Impedance: Measured pacing impedances with values $\leq 200 \Omega$ or $\geq 2000 \Omega$

Adverse Event: Any unfavorable clinical event which impacts, or has the potential to impact the health or safety of a patient caused by or associated

with a study device or intervention. Adverse events are classified as complications or observations.

Cardiac Tamponade: Confirmed or suspected accumulation of fluid in the pericardial space.

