All patients who had an attempted implant of the QuickFlex μ 1258T LV Lead will be included in the analysis of this endpoint. The survival time for all patients will be calculated as the number of days from implant or attempted implant to the date the complication was first discovered. For patients who do not experience a complication related to the LV lead at the time of their withdrawal, the survival time will be censored on the date of their withdrawal. For patients who have not experienced any complication related to the LV lead at the time of analysis, the survival time will be censored on the date of analysis. This analysis will also include all IDE study patients from sites that agree to participate in the PAS study. Patients from these sites who participated in the IDE study, but who do not consent to participate in the PAS study will be included in the analysis. If event free, they will be censored at the time of approval of the QuickFlex μ 1258T LV Lead or the last IDE follow-up visit (whichever is later). This will ensure that there is no bias in the estimates of complication rates; site selection criteria are independent of complication rates. The endpoint will be evaluated using the Kaplan-Meier method and the 95% lower confidence bound (LCB) will be obtained by transformation from its log scale, based on Peto et al². The null hypothesis will be rejected if the 95% LCB is greater than 92.5%. Kaplan-Meier curves will also be presented for each adverse event category of complication listed above.

A sub-group analysis will be performed to compare the LV lead related complication rates in patients rolled over from the IDE study to newly enrolled patients. Complication free survival estimates will also be estimated for the newly enrolled and IDE subjects by stratification in the Kaplan Meier analysis. The two groups will be compared using the log-rank test. As with the primary analysis, the sub-group analysis will include all IDE study patients from sites that agree to participate in the PAS study. Patients from these sites who participated in the IDE study, but who do not consent to participate in the PAS study will be included in the analysis. If event free, they will be censored at the time of approval of the QuickFlex μ 1258T LV Lead or the last IDE follow-up visit (whichever is later). This will ensure that there is no bias in the estimates of complication rates; site selection criteria are independent of complication rates.

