4.5.1.3 Unsuccessful Implant

Patients who have an unsuccessful implantation of a St. Jude Medical CRT-D system will be followed for a period of 30 days for adverse events and then withdrawn from the study unless the implant will be re-attempted.

Complete Patient Status, Enrollment, Implant and Product Out of Service (if applicable) Case Report Forms and record all results. If an adverse event or protocol deviation occurred during the attempted implant procedure, complete an Adverse Event and/or Deviation Case

Report Form. Send the forms to St. Jude Medical, CRMD Sunnyvale, CA.

After 30 days, complete a Withdrawal Case Report Form and Adverse Event Case Report Form (if applicable) and record all results. Send the forms to St. Jude Medical, CRMD Sunnyvale, CA.

If the physician chooses to re-attempt the implantation of a St. Jude Medical CRT-D system, complete an Implant Case Report Form and Product Out of Service Case Report Form (if applicable) and record all results. If an adverse event or protocol deviation occurred during the implant procedure, complete an Adverse Event and/or Deviation Case Report Form. Send the forms to St. Jude Medical, CRMD Sunnyvale, CA.

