10.0 Withdrawals

Withdrawal is defined as termination of participation of a patient from a clinical trial. All reasonable efforts should be made to retain the subject in the clinical trial until completion of the clinical trial. Reasons for withdrawal include, but are not limited to the following:

- Heart Transplant
- Patient Death
- Patient and/or Family Request
- Patient Lost to Follow-Up - Defined as the following: Patient will be considered "lost to follow-up" after a minimum of two documented phone calls were made by personnel at the study center to the patient or emergency contact, a certified letter was sent to the last known address, and two consecutive visits pass without an investigator receiving data
- Patient Non-compliance
- Patient Participation terminated by Investigator
- Sponsor Request
- System explanted without a system replacement
- Unsuccessful Implant
- Removal of the QuickFlex® μ 1258T lead without a QuickFlex® μ 1258T lead replacement

Complete a Withdrawal Case Report Form and record all results. If the patient experienced an adverse event or protocol deviation, complete an Adverse Event and/or Deviation Case Report Form. Send the forms to St. Jude Medical, CRMD Sunnyvale, CA.

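### The final-report complication rates at 5 years are crude binomial proportions over all attempted implants, so with about 45% planned non-evaluable they fall below the Kaplan-Meier 5-year risk of Endpoint 1

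*Protocol*

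**What the plan says.** Section 4.2.3 of the protocol fixes both the statistic and the denominator. Its Final Report paragraph presents counts and proportions for each Table 2 complication type at 5 years, "along with the 95% confidence intervals for the proportion based on the Clopper-Pearson exact Binomial method". The patient group is "All patients who are implanted or attempted to be implanted with the" study lead. The same complications are to be "reported and summarized for all patients and will also be broken out by gender". No minimum follow-up or censoring is stated.

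Other sections show that many of these patients will not be observed for 5 years:

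- Section 4.1: "There will be 1,884 new patients enrolled in the study to achieve an evaluable sample size of 1036 patients".
- Section 4.5.1.3: failed implants are followed for 30 days "and then withdrawn from the study unless the implant will be re-attempted". They remain in the 4.2.3 denominator.
- Section 10.0 lists "Patient Death" among the withdrawal reasons, together with loss to follow-up, patient request, non-compliance and others.

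Section 4.2.1 applies a different method to the same list of complications. Endpoint 1 is estimated by Kaplan-Meier, and for a patient who withdraws event-free "the survival time will be censored on the date of their withdrawal". It adds that "Kaplan-Meier curves will also be presented for each adverse event category of complication listed above".

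**The concern.** A patient who leaves event-free at month 8 counts in 4.2.3 as a patient without a complication at 5 years. That is not known. The proportion therefore does not estimate the 5-year risk targeted by Endpoint 1, and the Clopper-Pearson interval, which is exact only for fully observed outcomes, is centred on too low a value.

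The final report would then show two 5-year figures for the same complications: 1 minus Kaplan-Meier under 4.2.1 and a lower percentage under 4.2.3, with nothing to explain the gap. The study exists to characterise long-term lead performance, so an understatement that is greatest for late failures is the wrong direction of error. What is at stake is the accuracy of the reported rates. No test or decision rule is visibly attached to this objective.

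**Working it through.** **Inputs from the protocol.** 1,884 new patients and 1,036 evaluable (4.1); total sample 1,955 to 1,991 (4.1); Endpoint 1 goal 92.5%, whose complement is 7.5% (4.2.1); complication rate 0.4% in the Appendix B simulation.

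**The plan's own figure.** 1 − 1,036/1,884 = 0.4501. In reverse, 1,036/(1 − 0.45) rounds up to 1,884, so the two stated numbers agree with 45% attrition. This does not check 1,036 itself, whose derivation is blacked out.

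**Assumptions.** The visible text does not split the 45% by time or cause. The base case takes attrition at a constant rate over 5 years, applied to all patients: ha = −ln(1,036/1,884)/5 = 0.1196 per year.

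**Direction.** On the same data, events/N can never exceed 1 minus Kaplan-Meier. It is lower whenever a patient is censored before a later event.

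**Size, constant complication hazard.** For a 5-year risk F with death censored, he = −ln(1 − F)/5, and the expected crude proportion is he/(he + ha) × (1 − exp(−5(he + ha))). For F = 7.5%, he = 0.01559, and the crude value is 0.01559/0.13520 × (1 − exp(−0.6760)) = 5.67%.

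Coverage below is the probability that the nominal 95% Clopper-Pearson interval contains F, summed exactly over the binomial distribution with N = 1,955. The last column places half of the events at implant and the rest at a constant hazard.

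| Kaplan-Meier risk F | Crude proportion | Shortfall | Coverage, constant hazard | Coverage, half at implant |
|---|---|---|---|---|
| 0.4% | 0.301% | 25% | 93% | 96% |
| 1% | 0.753% | 25% | 87% | 95% |
| 2% | 1.51% | 25% | 70% | 91% |
| 5% | 3.77% | 25% | 28% | 79% |
| 7.5% | 5.67% | 24% | 11% | 68% |

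With N = 1,991 the constant-hazard coverage is 94% at 0.4%, 67% at 2%, 26% at 5% and 9% at 7.5%.

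**Sensitivity to timing (shortfall against 1 minus Kaplan-Meier).**

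- 25%, 50% or 75% of events at implant: 18%, 12% or 6%.
- Falling hazard (Weibull shape 0.5): 17%.
- Late-rising hazard (shape 2 to 3): 32% to 36%.
- Extreme case, all attrition at the start: 45% (7.5% read as 7.5% × 0.55 = 4.1%).

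**Sensitivity to cause of attrition.** Against cumulative incidence with death as a competing event (death hazard d × ha), the shortfall is 19%, 13%, 7% or 0% if 25%, 50%, 75% or 100% of attrition is death.

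**The case against.** The case on the other side has five parts.

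1. *Other outputs already adjust for follow-up.* Section 4.2.1 plans Kaplan-Meier curves by category and estimates stratified by IDE versus new patients, and Table 2 has a per-patient-year column. This stands and narrows the gap to the 5-year percentage and interval per type, the percentage in the Total row, and the gender breakdown. It does not correct those figures.
2. *Section 4.2.3 names no risk as its target.* The time reference could mean when the report is written, and Table 2 heads its column as a percentage of patients. That reading is possible, but a rate at 5 years with a confidence interval will naturally be read as a 5-year risk. The patient group offers no rescue: Endpoint 2 is restricted to patients who complete 5 years, and 4.2.3 is not.
3. *Death is a competing event.* If all attrition were death, the crude proportion would be the cumulative incidence. With half of it death, coverage against cumulative incidence is 97% at 0.4%, 95% at 1% and 90% at 2%. This stands as a limit on size. The protocol lists several withdrawal reasons other than death, so no bias at all is unlikely.
4. *The lowest coverage figures belong to a total.* The 7.5% is for all types combined, while the interval is specified per type. Seven types sharing 7.5% average about 1% each, where coverage is 87% to 95%. At 0.4% the shortfall is 0.1 percentage point, and a typical interval (6 events in 1,955: 0.11% to 0.67%) still contains 0.4%. This stands: rare types are little affected. The early-event scenarios, however, cannot apply to dislodgement, which counts only after 30 days.
5. *Kaplan-Meier by type has its own awkwardness.* Lead removal without replacement ends follow-up, so one complication can censor another, and type-specific values need not add up to the total. This is true and worth a footnote, but the category curves in 4.2.1 already carry it.

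**Conclusion.** The concern holds. As written, 4.2.3 reports as a rate at 5 years a proportion that is low against the Kaplan-Meier target set in 4.2.1 for the same complications. The direction against that target is certain once any patient is censored before a later event.

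The size rests on assumptions. It is about 25% in relative terms with constant attrition and constant hazard, 6% to 18% if a quarter or more of the events occur at implant, and 32% to 36% if failures come late. It shrinks towards zero against cumulative incidence as the share of deaths in the attrition rises. Applying 45% to the whole sample, including IDE patients, is also an assumption, because the figure concerns new patients.

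The effect is modest for rare types and material for commoner types and the total. The objective is descriptive and Endpoint 1 handles censoring properly, so this should be corrected but threatens no primary conclusion.

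**What to change.** State one target in the Final Report paragraph of 4.2.3 and use it throughout. Suggested text:

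> For each complication type in Table 2, for the total, and by gender, the 5-year rate is 1 minus the Kaplan-Meier estimate at 5 years, with the time axis and censoring of section 4.2.1 and a two-sided 95% confidence interval on the log-log scale. For rows with no events, an exact Poisson upper limit per patient-year is given.

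Keep the counts and the complications per patient-year. Label the Table 2 percentage of patients as a crude percentage, not a 5-year rate. If cumulative incidence with death as a competing event is preferred, name it as the target and say that it differs from Endpoint 1.

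The cost is wording only. The per-type estimates come from analyses already planned in 4.2.1, and only the gender split is added. Reported rates will be somewhat higher and their intervals wider.

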4.2.4 Additional Data

- Demographic data including gender, age, ethnicity, tobacco use, cardiovascular history, arrhythmia history, NYHA functional classification, left ventricular ejection fraction, QRS duration, cardiomyopathy classification, cardiac medications, and continuous variables will be summarized by average and standard deviation. Categorical variables will be summarized by frequency and percentage.
- Capture thresholds using a pulse width of 0.5ms for LV leads at enrollment/implant and at each follow-up visit – the average threshold along with standard error bars will be plotted for each visit. LV threshold testing must be performed in bipolar configuration.
- Pacing lead impedance for LV leads at enrollment and at each follow-up visit – the average lead impedance along with standard error bars will be plotted for each visit. LV threshold testing must be performed in bipolar configuration.
- LV lead handling characteristics
- LV lead implanting tools/accessories
- LV lead venous access location
- LV lead implant attempts and repositions during procedure
- LV lead implant procedure and fluoroscopy time

- Final LV lead location
- Final programming for LV pacing configuration
- Reasons for unsuccessful LV lead implant
- Mortality
- Adverse Events
- LV lead implant attempts – the average, standard deviation and range of number of LV lead implant attempts will be reported
- Mortality – a Kaplan-Meier analysis will be performed for all-cause death
- Adverse Events will be classified and reported as complications or observations. Interim and Final reports will summarize all adverse events. Observations and complications will also be classified as related to the LV lead or unrelated to the LV lead and reported in the following categories.
 - a. LV lead related complications include:
 - i. Diaphragmatic/Phrenic nerve stimulation
 - ii. Lead dislodgement that occurred greater than 30 days after implant
 - iii. Lead insulation damage
 - iv. Lead fracture
 - v. Elevated pacing threshold
 - vi. Loss of capture
 - vii. Cardiac perforation
 - viii. Other unexpected complications that are considered related to the LV lead
 - b. Complications that are unrelated to the LV lead include:
 - i. Pneumothorax
 - ii. Infection
 - iii. Bleeding/Hematoma requiring pocket revision
 - iv. Cardiac Perforation
 - v. CS dissection/perforation
 - vi. Cardiac vein thrombosis
 - vii. Lead dislodgement occurring in the peri-operative period (within 30 days of implant)
 - viii. Elevated pacing thresholds due to patient's venous anatomy
 - ix. Loss of capture unrelated to lead fracture or dislodgement
 - x. Abnormal Lead pacing impedance ($\leq 200 \Omega$ or $\geq 2000 \Omega$) unrelated to lead fracture or dislodgement
 - xi. Complications related to other implanted leads (right atrial or right ventricular)

4.3 Site Selection

Centers will be selected for participation in the study based on their ability to screen and enroll eligible patients, and perform the required study procedures outlined in sections 4.5 and 4.5.1. SJM will attempt to have a diversified group of centers participating in the study in the United States, including academic and non-academic institutions, [REDACTED]. To ensure a widespread distribution of data and minimize site bias, a maximum of approximately 15% of the total enrollment will be allowed at a single site.

The sites who have participated in the QuickFlex® μ 1258T Investigational Device Exemption (IDE) study will be invited to participate in this post market study. Sites who agree to participate will be instructed to approach all patients who were previously enrolled in the QuickFlex® μ 1258T Investigational Device Exemption (IDE) study for participation in the post market study for further data collection.

4.4 Patient Selection

4.4.1 Inclusion Criteria

Eligible patients will meet **all** of the following:

1. Have an approved indication per ACC/AHA/HRS guidelines for implantation of a CRT-D system or participated in the QuickFlex® μ 1258T IDE study
2. Have the ability to provide informed consent for study participation and be willing and able to comply with the prescribed follow-up tests and schedule of evaluations

4.4.2 Exclusion Criteria

Patients will be excluded if they meet **any** of the following:

1. Have a hypersensitivity to a single 1.0mg dose of dexamethasone sodium phosphate or short term contact with heparin
2. Have a life expectancy of less than 5 years due to any condition
3. Be less than 18 years of age

4.5 Study Procedures

All required study procedures at each specified interval are outlined in the sections below.

Table 3: Schedule of Evaluations Summary

Evaluation	Enrollment/ Implant	6 months	12months	Every 6 months through 5 years
Inclusion/Exclusion Evaluation	√			
Bipolar LV Lead capture threshold testing using a pulse [contact] ms and LV lead impedance. Bipolar pacing configuration is required.	√	√	√	√
**Unipolar LV lead capture threshold testing using a pulse [contact] ms and LV lead impedance. Only for patients programmed to LV unipolar pacing configuration	√	√	√	√
Real time measurements and trends for all implanted leads	√	√	√	√

4.5.1 Enrollment Requirements

4.5.1.1 Enrollment

Patients will undergo screening evaluations as outlined by the inclusion/exclusion criteria. The proportion of male and female patients enrolled over time will be carefully monitored to ensure a representative sampling that is consistent with clinical practice. In both the SJM sponsored Post Approval Study, and the Attain Model 4193 LV lead study, male patients comprised 60%-70% of the study cohort. It is expected that the proportion of male patients in this study will be comparable.

Data will be collected on the patient's gender, age, ethnicity, tobacco use, cardiovascular history, arrhythmia history, NYHA functional classification, left ventricular ejection fraction, QRS duration, cardiomyopathy classification, and cardiac medications.

Patients who meet inclusion/exclusion criteria, sign an IRB/MEC approved informed consent, and have an implant or attempted implant of the QuickFlex® μ 1258T LV lead will be considered enrolled in the

study. The enrollment date for patients in the study will be the date of implant or attempted implant.

The IDE cohort patients will be eligible to rollover into the post approval study after signing consent for further data collection. The enrollment date for these patients will be the date of signing consent.

Complete and submit a Patient Status, Enrollment and Implant Case Report Form(s). If an adverse event or protocol deviation occurred during this visit, complete an Adverse Event and/or Deviation Case Report Form. Send the forms to St. Jude Medical, CRMD Sunnyvale, CA.

*Do not complete an Enrollment or Implant Case Report Form for the IDE rollover patients.

